6.1 Recruitment and Enrollment of Subjects

1. Recruitment Sites: The study will be conducted in three tertiary grade A hospitals (Shandong Provincial Hospital, Jinan Central Hospital, Beijing Anzhen Hospital). All centers have qualified 3.0T CMR equipment, standardized stress perfusion scanning protocols, and experienced cardiology and radiology teams to ensure the accuracy and consistency of MVD assessment.
2. Recruitment Methods: Subjects will be recruited through outpatient clinics, inpatient wards, and referrals of the Cardiology Department of each research center. Researchers will explain the purpose, process, potential risks, and benefits of the study to potential subjects in detail, and provide written informed consent forms. Only those who fully understand and voluntarily sign the informed consent form will be included in the study.
3. Enrollment Process: After signing the informed consent form, subjects will undergo baseline assessment (including clinical data collection, laboratory tests, electrocardiogram, and stress perfusion CMR examination). Researchers will review the inclusion and exclusion criteria again based on the assessment results, including confirmation of DCM diagnosis according to WHO/ISFC criteria and exclusion of subjects with infarct patterns of LGE or significant CAD. Qualified subjects will be assigned a unique study number, and relevant information will be recorded in the case report form (CRF).

6.2 Baseline Assessment

1. Clinical Data Collection: Researchers will collect general information (age, gender, height, weight, body mass index [BMI], smoking history, drinking history, family history of cardiovascular diseases, etc.), medical history (onset time, clinical symptoms, previous treatment history, ICD implantation status if any, etc.), and medication history (type, dosage, course of treatment, etc.) of subjects through questionnaires and medical record review.
2. Laboratory Examinations: Venous blood will be collected from subjects on an empty stomach (fasting for ≥ 8 hours) to detect indicators such as N-terminal pro-B-type natriuretic peptide (NT-proBNP), troponin I/T, creatinine, liver function (alanine aminotransferase, aspartate aminotransferase, total bilirubin), electrolytes (potassium, sodium, chlorine), and fasting blood glucose. All tests will be performed by the clinical laboratory of each research

center in accordance with standard operating procedures (SOP).

3. **Electrocardiogram:** Resting 12-lead electrocardiogram will be performed for all subjects to record heart rate, rhythm, ST-T segment changes, and other indicators, which will be stored and archived.
4. **Stress Perfusion CMR Examination (Key Assessment for MVD):** All subjects will undergo CMR examination using a 3.0T magnetic resonance scanner (consistent model across all research centers). The examination includes two parts: ① Routine CMR sequences: Cine imaging (for measuring left ventricular end-diastolic volume, end-systolic volume, LVEF, etc., and calculating LVEDV/BSA for DCM diagnosis), T1 mapping, T2 mapping, and LGE imaging (for detecting myocardial fibrosis and identifying infarct patterns to exclude ischemic etiologies); ② Stress perfusion CMR: Adenosine (140 µg/kg/min) will be infused to induce myocardial stress, and first-pass perfusion imaging will be performed before and after stress to measure myocardial blood flow (MBF) at rest and during stress. Myocardial perfusion reserve (MPR) will be calculated as the ratio of stress MBF to rest MBF, with $MPR < 2.0$ defined as MVD according to established diagnostic criteria. Scanning parameters will be standardized across all research centers to ensure the consistency of image quality. CMR images will be stored in DICOM format for subsequent analysis. Two independent radiologists (with more than 5 years of experience in cardiac imaging) will review LGE images to confirm the absence of infarct patterns and independently assess MVD severity based on MPR values, with consensus reached through discussion in case of discrepancies. AI technology will be briefly used for auxiliary extraction of perfusion image features to improve the efficiency of MPR calculation, without in-depth model optimization.

6.3 Follow-up

1. **Follow-up Frequency and Time Points:** Follow-up will be conducted at 3 months, 6 months, 12 months, 18 months, and 24 months after baseline stress perfusion CMR examination. For subjects who experience the primary or secondary endpoint event, additional follow-up will be conducted for 6 months to record the recovery and long-term prognosis after the event. In addition, long-term follow-up will be conducted at 1 year, 3 years, and 5 years post-CMR to observe long-term outcomes.
2. **Follow-up Methods:** A combination of outpatient follow-up, telephone follow-up, and medical record review will be used. At each follow-up, researchers will record the occurrence of endpoint events (in detail for SCD-related events and secondary endpoint events), changes in clinical symptoms, medication adjustments, re-examination results (NT-proBNP, electrocardiogram, and CMR re-examination if necessary), and adverse events. For subjects with MVD at baseline, changes in MVD severity will be assessed by stress perfusion CMR re-examination at 12 and 24 months if clinically feasible.
3. **Endpoint Event Judgment:** An endpoint event judgment committee composed of 3 senior cardiologists will be established to review and confirm the occurrence of endpoint events. The committee will make a judgment based on medical records, examination results, and follow-up records, referring to the diagnostic criteria in Appendix S1 for SCD-related events, to ensure the accuracy and objectivity of the data. For SCD, the definition is death due to cardiac causes occurring within 1 hour of symptom onset with sudden loss of consciousness; for

appropriate ICD shock, it refers to shocks delivered in response to hemodynamically unstable ventricular tachycardia or fibrillation without reversible causes ; for resuscitated cardiac arrest, it refers to a cardiac arrest event reversed by cardiopulmonary resuscitation, defibrillation, or pacing .

6.4 Data Collection and Management

1. Data Collection: Researchers will fill in the CRF truthfully and completely according to the baseline assessment and follow-up results, with special emphasis on recording stress perfusion CMR indicators (rest MBF, stress MBF, MPR) and the occurrence of SCD-related events. CMR images, laboratory test reports, electrocardiograms, endpoint event records, and other relevant data will be archived in a unified manner.
2. Data Verification: The data management team will conduct double-entry and verification of the CRF data to correct errors and missing information in a timely manner. The completeness, accuracy, and consistency of MVD-related data and endpoint event records will be checked regularly (once a month) during the study period.
3. Data Storage: All study data (including CRF, CMR images, laboratory test results, and follow-up records) will be stored in a dedicated computer with password protection and data encryption to ensure the confidentiality and security of subjects' personal information. The data retention period will be at least 5 years after the end of the study, in accordance with relevant national regulations and ethical requirements.
4. Data Sharing: Individual participant data (IPD) will not be made available to external researchers. The dataset contains sensitive clinical, imaging, and longitudinal prognostic information from patients with DCM. Broad sharing of IPD may compromise patient privacy and confidentiality, violate informed consent restrictions, and increase the risk of re-identification. Therefore, IPD will be retained securely within the study group and will not be shared externally.

7. Auxiliary AI Application (Brief)

Artificial intelligence technology will be applied to support the analysis of stress perfusion CMR datasets, including automated image feature extraction and model construction. Professional image processing software incorporating basic artificial intelligence algorithms will be utilized to assist with left ventricular segmentation and the extraction of perfusion-related imaging features, such as signal intensity upslope gradients during gadolinium first-pass perfusion imaging. These features will support the calculation of resting myocardial blood flow (MBF), stress MBF, and myocardial perfusion reserve (MPR), with the goal of improving the efficiency and reproducibility of microvascular dysfunction (MVD) assessment.

Subsequent large-scale development, optimization, and independent validation of artificial intelligence models will be performed in this study. The primary objective remains the evaluation of the predictive value of MVD, as assessed by stress perfusion CMR, for sudden cardiac death (SCD) – related adverse events.

8. Quality Control

1. **Personnel Training:** Before the start of the study, all researchers, radiologists, data managers, and study coordinators will receive unified training on the study protocol, SOP, data collection requirements, endpoint event judgment criteria, stress perfusion CMR scanning and MVD assessment standards, and ethical norms to ensure the consistency of operation.
2. **CMR Quality Control:** All research centers will use 3.0T magnetic resonance scanners of the same model, and the scanning parameters (including stress perfusion sequences) will be standardized. A professional CMR quality control team will regularly check the image quality (once every 3 months); unqualified images will be re-scanned if necessary, and subjects who cannot complete the stress perfusion CMR examination will be excluded from the study. The consistency of MVD assessment by radiologists will be tested using Kappa analysis, with Kappa value ≥ 0.80 required to ensure reliability.
3. **Data Quality Control:** The data management team will conduct regular inspections of the CRF data, with special focus on MVD-related indicators and endpoint event records, and any problems found will be fed back to the researchers in a timely manner for correction. The final data will be locked after verification to prevent data tampering. A random sample of 10% of the CRF data will be reviewed by the study leader to ensure data quality.
4. **Ethical Supervision:** The Ethics Committee of each research center will supervise the entire study process, review the study protocol and informed consent form regularly, and handle adverse events and ethical issues in a timely manner to ensure that the study is carried out in accordance with ethical principles.

9. Ethical Considerations

1. **Informed Consent:** All subjects will sign the informed consent form voluntarily after fully understanding the purpose, process, potential risks, and benefits of the study. The informed consent form will be provided in both Chinese and English (if necessary) to ensure that subjects can understand the content. Subjects have the right to ask questions about the study, and researchers will answer truthfully.
2. **Confidentiality of Subject Information:** The personal information of subjects (such as name, ID number, contact information) will be encrypted and stored, and will not be disclosed to any third party. The study data will be used only for scientific research purposes, and the identity of subjects will be anonymized during data analysis.
3. **Risk Management:** During the study, if subjects experience adverse events related to the study (such as contrast agent allergy during CMR examination, hypotension during adenosine infusion for stress perfusion), researchers will take timely and effective medical measures to ensure the safety of subjects. All adverse events will be recorded in detail and reported to the Ethics Committee and the study leader within 24 hours. For subjects with high risk of SCD-related events identified during follow-up (especially those with severe MVD), researchers will promptly inform the treating physician to adjust the treatment plan (e.g., considering ICD implantation).

4. Voluntary Withdrawal: Subjects have the right to withdraw from the study at any time without any reason, and their medical treatment will not be affected. The data of subjects who withdraw from the study will be retained and included in the final data analysis (unless the subject requests to delete the data).

10. Statistical Analysis

Statistical analysis will be performed using SPSS 26.0 and R software (version 4.2.0). Measurement data will be expressed as mean \pm standard deviation (SD) if normally distributed, or median (interquartile range, IQR) if abnormally distributed; comparison between groups will be performed using t-test, non-parametric test (Mann-Whitney U test, Kruskal-Wallis test) as appropriate. Count data will be expressed as rate (%) and compared using χ^2 test or Fisher's exact test. The Kaplan-Meier method will be used to draw the survival curve of subjects (for endpoint events), and the log-rank test will be used to compare the event rate between DCM patients with and without MVD. Multivariate Cox proportional hazards regression model will be used to screen the independent risk factors for SCD-related events and secondary endpoint events, with MVD (assessed by stress perfusion CMR) as the key independent variable. The receiver operating characteristic (ROC) curve will be used to evaluate the predictive efficacy of MVD for SCD-related events, and the AUC value will be calculated. $P < 0.05$ will be considered statistically significant. Subgroup analysis will be performed based on age, gender, LVEF, and MVD severity to explore the predictive value of MVD in different subgroups.

11. Study Schedule

Study Stage	Time Arrangement (Months)	Key Tasks
Preparation Stage	1–3	Finalize the study protocol, train researchers and related personnel (focusing on stress perfusion CMR scanning and MVD assessment), standardize CMR scanning parameters, establish the data management system, design Appendix S1 (diagnostic criteria for SCD-related events), and obtain ethical approval from each research center.

Recruitment and Baseline Assessment Stage	4–12	Recruit subjects, conduct baseline assessment (clinical data collection, laboratory tests, electrocardiogram, stress perfusion CMR examination), review inclusion/exclusion criteria, assess MVD using stress perfusion CMR (with brief AI auxiliary analysis), and complete data entry and verification.
Follow-up Stage	13–36	Conduct regular follow-up, record endpoint events and adverse events, perform stress perfusion CMR re-examination at 12 and 24 months (if feasible) to assess changes in MVD severity, update study data, and conduct long-term follow-up at 1 year, 3 years, and 5 years post-CMR.
Data Analysis and Report Writing Stage	31–36	Conduct statistical analysis of the study data (focusing on the correlation between MVD and SCD-related events), sort out the study results, write the study report and Appendix S1, and submit the report to the Ethics Committee and relevant departments.

12. Adverse Event Management

12.1 Definition of Adverse Events

Any untoward medical occurrence in a subject during the study period, regardless of whether it is related to the study, including but not limited to: adverse reactions caused by CMR examination (contrast agent allergy, claustrophobia attack, etc.), adverse reactions related to

stress perfusion (hypotension, bradycardia, asthma attack due to adenosine infusion), deterioration of DCM-related symptoms (worsening heart failure, arrhythmia, etc.), and other unexpected medical events (infection, accidental injury, etc.). Endpoint events (SCD-related events, secondary endpoint events) are not classified as adverse events but are recorded separately.

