12.2 Reporting of Adverse Events

Researchers will record the occurrence time, type, severity, handling measures, and outcome of adverse events in detail in the CRF. Mild and moderate adverse events will be reported to the study leader and the Ethics Committee within 24 hours; severe adverse events (such as death, severe allergy requiring emergency treatment, severe hypotension unresponsive to treatment) will be reported immediately (within 2 hours) to the study leader and the Ethics Committee, and a follow-up report will be submitted after the event is handled.

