Appendix S1: Diagnostic Criteria for SCD-Related Events

1. Sudden Cardiac Death (SCD): Death due to cardiac causes occurring within 1 hour of the onset of acute cardiac symptoms, characterized by sudden loss of consciousness. For unwitnessed deaths with clear evidence of cardiac etiology, it is classified as probable SCD .
2. Appropriate Implantable Cardioverter-Defibrillator (ICD) Shock: Shocks delivered by an ICD in response to hemodynamically unstable ventricular tachycardia (VT) or ventricular fibrillation (VF) that is not caused by reversible factors (such as electrolyte imbalance, drug effects) .
3. Resuscitated Cardiac Arrest: A cardiac arrest event that is reversed, usually by cardiopulmonary resuscitation (CPR), defibrillation, cardioversion, or cardiac pacing, with restoration of spontaneous circulation .

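### Section 12.1 takes all endpoint events out of adverse-event reporting with no exception for those provoked by study adenosine stress, and Appendix S1 lets a provoked arrest count towards the primary endpoint

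*Protocol*

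**What the plan says.** Section 12.1 opens with a wide definition of an adverse event: "Any untoward medical occurrence in a subject during the study period, regardless of whether it is related to the study". Among the stress reactions it gives as examples are "hypotension, bradycardia, asthma attack due to adenosine infusion". It closes by taking both composites out of that class: "Endpoint events (SCD-related events, secondary endpoint events) are not classified as adverse events but are recorded separately".

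Section 12.2 sends mild and moderate adverse events to the study leader and Ethics Committee within 24 hours. For the serious ones it says: "severe adverse events (such as death, severe allergy requiring emergency treatment, severe hypotension unresponsive to treatment) will be reported immediately (within 2 hours". Section 9, item 3, repeats the 24-hour rule: "All adverse events will be recorded in detail and reported to the Ethics Committee and the study leader within 24 hours". For endpoint events, section 14, item 2, asks the co-investigators only for timely reporting. It sets no deadline and names no recipient.

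Appendix S1 defines the three primary components. An appropriate ICD shock must answer an arrhythmia "that is not caused by reversible factors (such as electrolyte imbalance, drug effects". Resuscitated arrest carries no such condition: "A cardiac arrest event that is reversed, usually by cardiopulmonary resuscitation (CPR), defibrillation, cardioversion, or cardiac pacing", with circulation restored. The SCD definition has none either. Section 6.3, item 3, shows the same difference between the components.

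On repeat scans, section 6.3, item 2, says: "For subjects with MVD at baseline, changes in MVD severity will be assessed by stress perfusion CMR re-examination at 12 and 24 months". The plan makes this conditional on feasibility.

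**The concern.** Two things are at stake.

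**Safety reporting.** Adenosine stress is a study procedure, and section 9 treats hypotension during the infusion as a study-related adverse event. An arrest during the same infusion is graver, yet it meets an endpoint definition and so leaves the class of events to which the reporting clocks apply. Section 13 lets the Ethics Committee stop the study if risks exceed benefits. For that it needs to learn promptly of the most serious harm the procedure can do.

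**Endpoint validity.** The study asks whether MVD predicts SCD-related events. An arrest provoked by the stress agent is a drug effect. The protocol already treats drug effects as outside the target for ICD shock, but not for the other two components. Because repeat stress scans are planned for subjects with MVD at baseline, any provoked event would tend to be added to the group that the log-rank and Cox analyses (section 10) are expected to show at higher risk.

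**Working it through.** There is no plan figure to reproduce, so the check sets the rules side by side and follows each kind of event through them.

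1. **Lesser adenosine reaction (for example, moderate hypotension).** Adverse event under 12.1. Reported to the study leader and Ethics Committee within 24 hours (section 9, item 3, and 12.2).
2. **Resuscitated arrest during stress.** Meets Appendix S1, item 3, so 12.1 removes it from the adverse events. Neither clock covers it. Only the general duty in section 14 remains, with no deadline or recipient. Item 3 counts arrests reversed by pacing and 12.1 names bradycardia as an adenosine reaction, so a bradycardic arrest on adenosine fits the definition.
3. **Sudden cardiac or heart-failure death.** Not an adverse event under 12.1, but 12.2 lists death without qualification. Two readings are possible: all deaths get the 2-hour report, or only deaths outside the composites do. The text does not choose.
4. **Other death (for example, from infection).** Adverse event under both sections. No conflict.
5. **Event at the baseline scan.** Follow-up runs from after that scan (sections 2 and 6.3), a study number is assigned only after baseline assessment and eligibility review (section 6.1), and subjects who cannot complete the stress scan are excluded (section 8, item 2). It is unclear whether such an event counts as a primary endpoint.
6. **Arrest at a repeat scan.** It occurs after the baseline scan and meets Appendix S1 as written. The drug-effect exclusion does not reach it.

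**Direction and size.** Let p be the proportion with baseline MVD, which the protocol does not give. With 450 subjects (the planned minimum) and two repeat scans each, planned repeat stress scans in the MVD group number at most 450 × p × 2 = 900p. At an assumed p of 0.5 that is 225 × 2 = 450. This is a ceiling for a cohort of that size, since scans depend on feasibility and some subjects will die or withdraw.

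At an assumed two-year incidence of 5% to 10%, primary events number 450 × 0.05 = 22.5 to 450 × 0.10 = 45. One provoked event would then be 1/45 = 2.2% to 1/22.5 = 4.4% of the total. That is the weight of a single event, not an expected bias. The expected bias needs the rate of adenosine-provoked arrest, which the documents do not give.

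**The case against.** The strongest reply is that this is a narrow wording gap, and that four stronger readings fail. Much of that is right.

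- **A flat contradiction between 12.1 and 12.2, with provoked deaths escaping reporting.** A reader might infer both, but the documents support neither. Deaths outside the composites remain adverse events, so the word in 12.2 can be read consistently. If it is instead read to cover every death, a provoked death is reported within 2 hours. For endpoint deaths the text is ambiguous, no more.
- **No duty at all to report a provoked arrest.** Also too strong. Section 14 requires timely reporting of endpoint events, the endpoint committee reviews each one, and any hypotension or bradycardia before the arrest is itself reportable. What is missing is a deadline and a recipient for the arrest.
- **A baseline arrest counts as a primary event.** Not established, for the reasons in step 5 of the working. Moving the start of the endpoint clock would largely restate sections 2 and 6.3.
- **Repeat exposure exists only in the MVD group.** Section 6.3 names that group, but the schedule in section 11 lists the repeat stress scans without the restriction, and section 6.3 also allows CMR re-examination when necessary for any subject, without specifying stress. The defensible word is mainly.

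It is also fair to say that the bias may be negligible, and that sensitivity analyses are often left to the SAP. But the uneven exclusion is in Appendix S1 and the reporting gap is in section 12, so both need correcting in this protocol.

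**Conclusion.** The point holds in a limited form. An adenosine-provoked resuscitated arrest has no stated reporting deadline or recipient, although milder reactions to the same infusion have both. For SCD and heart-failure deaths, the application of the 2-hour rule is ambiguous. At a repeat stress scan, a provoked arrest meets the primary endpoint because the drug-effect exclusion covers ICD shock alone.

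The bias would run towards an association between MVD and SCD-related events, on the assumption that repeat stress scans take place mainly in the MVD group, as section 6.3 plans. Its size is unknown: provoked events are probably few, and no rate is given. The case for change rests on the reporting gap and the uneven endpoint definition, not on a demonstrated distortion of the result.

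**What to change.** Reconcile sections 12.1 and 12.2 with Appendix S1.

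1. In 12.1, state that any death, and any endpoint event that starts during or is attributed to a study CMR examination, is reported under 12.2 as well as being recorded and adjudicated as an endpoint.
2. In Appendix S1, and in the matching text of section 6.3, apply the drug-effect and reversible-cause exclusion to all three primary components for events provoked by study stress. Have the existing endpoint committee flag such events, leave them out of the primary analysis, and add a sensitivity analysis that counts them.

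The cost is protocol wording, one adjudication field, one extra analysis and a few more expedited reports. The scans and the sample size do not change.
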